This trial will recruit healthy participants with opioid use disorder (N=16, completers).

Testing will begin following stabilization on oral morphine (120 mg/day), which will continue throughout the trial. During each testing session, a single V-MJ + naloxone dose combination will be assessed (in randomized order), with **24 hours** between testing sessions. Laboratory testing sessions will consist of a modified naloxone challenge procedure, which quantifies the severity of naloxone-precipitated opioid withdrawal (Jones et al., 2019).

The slow rate of onset for oral cannabinoid administration would not have utility in an emergency. Therefore, the rapid pharmacodynamics of vaporized marijuana will allow the investigators the opportunity to investigate the potential utility of an ecologically valid combined cannabinoid + NLX opioid overdose emergency intervention. The investigators hypothesize that the combined administration (V-MJ + NLX) will produce significantly less withdrawal than NLX alone.

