## **Description of Subject Population**

### Sample #1

Specify subject population

Opioid-Dependent Participants with Opioid Use Disorder

Number of completers required to accomplish study aims

16

Projected number of subjects who will be enrolled to obtain required number of completers

32

Age range of subject population

18-55

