	Admission	Stabilization	Stabilization	Stabilization	Stabilization	Stabilization	Stabilization	Stabilization	Stabilization	Stabilization	NLX 0mg + V-MJ 0mg	NLX 4mg + V-MJ 25mg		
Week 3							Week 4							
	NLX 0mg + V-MJ 12.5mg	NLX 0mg + V-MJ 25mg	NLX 4mg + V-MJ 12.5mg	NLX 4mg + V-MJ 0 mg			Discharge							

**Laboratory Testing:** Laboratory testing sessions will consist of a modified naloxone challenge procedure (A.K.A. Wang Test: Wang et al., 1974). The challenge begins with baseline assessments. Ten common symptoms of opioid withdrawal (gooseflesh, vomiting, tremor, sweating, restlessness, lacrimation/nasal congestion, yawning, warming/cooling sensations, stomach pain, and muscle ache) will be assessed by a research assistant trained in administering the SOWS/COWS. For safety, the physician or nurse who is providing medical oversight will directly observe its administration.

Each symptom is coded as either “absent” or “present,” with between 1 and 6 points added when a symptom is observed (Table 2). Following pre-test assessments, a physician or nurse practitioner will administer the study drug combination (1000-1100 hrs). Assessments of withdrawal are made at 10-minute intervals for 50 minutes. The total withdrawal score is calculated at the end of the session. To minimize carry-over effects, sessions will be conducted at least 48 hours apart (>5 half-lives of both medications). See Table 1 for an example dosing schedule. The following dose combinations of vaped marijuana (V-MJ) and IN naloxone will be tested in random order:

- Naloxone 0 mg + V-MJ 0.0 mg
- Naloxone 0 mg + V-MJ 12.5 mg
- Naloxone 0 mg + V-MJ 25 mg
- Naloxone 4 mg + V-MJ 0.0 mg
- Naloxone 4 mg + V-MJ 12.5 mg
- Naloxone 4 mg + V-MJ 25 mg

Signs and Symptoms	Table 2: Rating Scale for Opioid Withdrawal											
	(Pre-test)		Time after first naloxone dose									
	0 min		10 min		20 min		30 min		40 min		50 min	
Signs and Symptoms	Present	Absent	Present	Absent	Present	Absent	Present	Absent	Present	Absent	Present	Absent
Gooseflesh	6	0	3	0	3	0	2	0	1	0	1	0
Vomiting	6	0	3	0	3	0	2	0	1	0	1	0
Tremor	6	0	3	0	3	0	2	0	1	0	1	0
Sweating	6	0	3	0	3	0	2	0	1	0	1	0
Restlessness	4	0	2	0	2	0	1	0	1	0	1	0
Lacrimation/ Nasal Congestion	4	0	2	0	2	0	1	0	1	0	1	0
Yawning	4	0	2	0	2	0	1	0	1	0	1	0
Feeling of Change in Temperature	3	0	1	0	1	0	1	0	1	0	1	0
Stomach Pain	3	0	1	0	1	0	1	0	1	0	1	0
Muscle Ache	3	0	1	0	1	0	1	0	1	0	1	0
Actual time of observation												
Scores												
Pupil Diameter												

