STATISTICAL ANALYSES

Data Analysis Plan: The distributions of all continuous variables will be checked for normality, and transformations will be employed (if necessary) before applying specific parametric techniques. Before performing specific analyses, we will examine all outcomes for outliers. All statistical comparisons will be two-sided and the critical level for rejection of the null hypothesis will be considered to be a p-value of < 0.05 . Where needed, False Discovery Rate Analysis will be used to adjust critical p values to control for multiple comparisons. Any comparison where homogeneity is violated will not be considered significant. Means, standard deviations, proportions, and 95% confidence intervals will be used to describe all continuous variables.

Dropouts and Missing Data: As this is an inpatient laboratory study within a controlled setting, we expect only minimal intermittent missing data, though we do expect to have some subjects drop out without completing all of the experimental conditions. We will use all available data from subjects prior to drop-out. We will account for missing data directly using mixed-effects models (MEM) (Diggle et al. 2002). MEMs do not require complete measurements to estimate effects and inferences are valid provided that data are “missing at random” (Little & Rubin, 2002). ‘Missing at random’ (i.e. the missing mechanism does not depend on the value of the unobserved outcome) is un-testable in most medical research and in our study as well. One can assume either parametric or semi-parametric models for the missingness that does depend on the unobserved outcome value and do the analysis (Diggle and Kenward 1994, Kenward 1998). Comparison of the inferences from assuming various models for the missingness provides a measure of the validity of the efficacy estimate from the model that assumes missing ‘at random’. One can also compute a local sensitivity index which measures the change in the estimated treatment effect in a neighborhood of the ‘missing at random’ model for missingness (Rotnitzky et al. 1998). We will perform sensitivity analyses based on these two approaches to assess the effect of the assumption of missing ‘at random’ on the inference.

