Randomization: Once a participant is enrolled, a randomization sequence table will be generated by a blinded statistician. The table will determine the order of testing of the various dose combinations of dronabinol (.00, .35, and .70 mg), and naloxone (0.0, 0.2 and 0.4 mg).

Aims, Outcome Measures, and Hypotheses

Primary Aim: Assess the ability of inhaled dronabinol to alter the severity of naloxone-precipitated withdrawal.

- The primary dependent variable (DV) for this aim will be the total opioid withdrawal score from the testing session. Repeated-measures analysis of variance (ANOVA) will be used to assess differences among the various dose conditions.
- We hypothesize that there will be a dose-dependent effect of dronabinol to attenuate the severity of naloxone-precipitated withdrawal.

Secondary Aim: Assess the safety of inhaled dronabinol in combination with naloxone.

- The primary DVs are the SAFTEE (AEs not related to withdrawal) and physiological parameters. Generalized mixed-effects models with participant as a random effect and an autoregressive correlation structure for the within-participant observations will be used to analyze the total number of AEs and their severity.
- We hypothesize that dronabinol, in combination with naloxone, will produce more AEs than placebo but less than naloxone alone.

Secondary Aim: Assess the impact of inhaled dronabinol on naloxone's effects on pupil diameter (i.e., μ -opioid receptor blockage).

- The primary DV will be pre-to-post- medication change in pupil diameter from each testing session. Repeated-measures ANOVA will be used to assess differences among the various dose conditions.
- We hypothesize that dronabinol will not significantly alter naloxone's effects on pupil diameter (in comparison to placebo).

Secondary Aim: Assess the abuse potential of inhaled dronabinol.

- The primary DV will be pre-to-post- medication change in positive subjective drug ratings such as drug "Liking" and "Good Effect."
- We hypothesize that self-reported dronabinol "Liking" will not be significantly greater than placebo.

Power

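### The SAP promises mixed models on all pre-dropout data but names repeated-measures ANOVA for the primary and pupil outcomes; in its standard form that ANOVA cannot keep the promise

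*SAP*

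**What the plan says.** The SAP's Dropouts and Missing Data paragraph applies to the whole study. It anticipates dropout during testing ("we do expect to have some subjects drop out without completing all of the experimental conditions") and commits to keeping what was observed: "We will use all available data from subjects prior to drop-out". It also names the tool: "We will account for missing data directly using mixed-effects models (MEM"). It adds two kinds of sensitivity analysis around the missing-at-random assumption.

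Under Aims, Outcome Measures, and Hypotheses, the primary aim (total withdrawal score) is assigned a different method: "Repeated-measures analysis of variance (ANOVA) will be used to assess differences among the various dose conditions". The pupil-diameter aim gets the same sentence. Only the adverse-event aim is given a mixed model: "Generalized mixed-effects models with participant as a random effect and an autoregressive correlation structure for the within-participant observations".

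The SAP states no analysis set, imputation rule or deletion rule for the ANOVA. Its Power section counts completers only.

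In the protocol, Study Procedures lists six V-MJ and naloxone combinations per participant ("The following dose combinations of vaped marijuana (V-MJ) and IN naloxone will be tested in random order"). Under Sample #1 the required number of completers is 16, and the entry for "Projected number of subjects who will be enrolled to obtain required number of completers" is 32.

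**The concern.** A standard repeated-measures ANOVA over six conditions needs six values per participant. One missed session removes the person, including the sessions that were completed. An analyst who follows the aims section literally would analyse completers only. One who follows the missing-data paragraph would fit a mixed model to everyone tested. The two can give different primary results, and the SAP does not say which governs, so the choice could be made after the data are seen.

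Three things are at stake.

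- **Precision.** Sessions already run would be discarded in a trial sized at 16 completers.
- **Selection.** If people who react badly are more likely to leave, completers are a selected group and the estimated V-MJ benefit shrinks.
- **Sensitivity analyses.** The planned missing-at-random checks presuppose a model that assumes missing at random for the efficacy outcome, and a complete-case ANOVA is not such a model.

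For pupil diameter the hypothesis is that V-MJ makes no significant difference, so lost precision makes that hypothesis easier to support.

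**Working it through.** **Inputs from the documents.** 16 completers and 32 projected enrolled (Protocol, Sample #1); six conditions in random order (Protocol, Study Procedures); a 15-point difference, SD 20, d = 0.75, stated power 90% (SAP, Power); two-sided alpha 0.05 (SAP, Data Analysis Plan).

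**Step 1: enrolment.** (32 − 16)/32 = 50% are projected not to complete; 16/(1 − 0.5) = 32 agrees.

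**Step 2: the plan's own power figure.** Read SD 20 as the SD of the paired difference. SE = 20/√16 = 5.00; noncentrality = 15/5.00 = 3.0; df = 15. Two-sided power is 0.80 (normal approximation 0.85). The stated 90% is not reproduced two-sided; one-sided gives 0.89 (t) or 0.91 (normal). It would also follow two-sided if SD 20 describes single scores and the within-person correlation is about 0.63, but no correlation is stated. That discrepancy is a separate point. Here 0.80 is the completers-only baseline.

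**Step 3: precision with all observed sessions.** The documents do not say when non-completers leave, so this is an assumed range. Model: random intercept, residual variance 20²/2 = 200, within-person correlation 0.3 to 0.7, dropout at random, 16 completers plus 16 non-completers. Effective n = 400/SE².

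| Assumed exit of the 16 non-completers | SE of contrast | Effective n | Power for 15 points |
|---|---|---|---|
| All before session 1 | 5.00 | 16 | 0.80 |
| Half before session 1, half after 1–5 sessions | about 4.55 | about 19 | about 0.87 |
| After 0–5 sessions, uniform | about 4.3 | about 21.5 | about 0.90–0.92 |
| After 1–5 sessions, uniform | about 4.2 | about 22.5–23 | about 0.91–0.93 |

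In the last row, completers supply 16 × 6 = 96 sessions and non-completers 16 × 3 = 48 on average, so a completers-only analysis discards 48 of 144. In the second row it discards 8 × 3 = 24 of 120.

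**Step 4: bias.** Simulation with assumed means of 5 in the three naloxone-0 conditions and 45, 37.5 and 30 under naloxone 4 mg with V-MJ 0, 12.5 and 25 mg. Between- and within-person SDs are both 14.14, so the paired-difference SD is √2 × 14.14 = 20. The true difference (V-MJ 25 mg against 0 mg) is −15. After each session the log-odds of leaving rise linearly with the score just observed, and enrolment continues to 16 completers.

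| Slope per point | Odds of leaving per 10 points higher | Completers-only bias toward zero |
|---|---|---|
| 0 | ×1 | 0% |
| 0.05 | × exp(0.5) = 1.65 | about 2% (80% completing) to 4% (50% completing) |
| 0.10 | × exp(1.0) = 2.7 | about 10% |
| 0.20 | × exp(2.0) = 7.4 | about 16% |

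A 16% bias turns −15 into −15 × 0.84 = −12.6. Across these mechanisms completers-only power was about 73–81%. The mixed model reached about 86–93% when non-completers contributed sessions, and its estimates stayed close to −15. With 300 runs the Monte Carlo error of a mean estimate is 5/√300 = 0.29 points, about 2% of 15, so differences of a point or two in the bias column are noise.

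**The case against.** The strongest reply is that the SAP nowhere says dropouts will be deleted. Its missing-data paragraph says the opposite, precedes all the aims and is not limited to adverse events. Its sensitivity analyses are framed around the efficacy estimate, which points to the withdrawal score. A repeated-measures ANOVA can also be obtained as a set of tests from a mixed model, which would reconcile the two sections. All of this stands: a reader might infer a deliberate plan to discard dropouts, and the documents do not support that. What remains is that the SAP never links the two sections, and it names a mixed model separately for adverse events, which suggests ANOVA means something else. Even on the generous reading the text needs a clarifying sentence.

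A reader might also infer that half of the trial's data would be lost. The 16 of 32 is a planning projection for enrolment. The protocol discharges people who cannot be stabilised on morphine and discontinues those who breach vital-sign limits in the safety session. Both exits precede any test session, and neither method can use those people.

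Finally, it is tempting to say that dropout is driven by severe withdrawal under naloxone alone and biases the result by 13–16%. That size needs a slope of roughly 0.14–0.20 per point. The protocol's session-linked rule for leaving the trial rests on vital signs or the BPRS in two discontinued V-MJ plus naloxone sessions, not on the withdrawal score. Voluntary exit after a bad session is plausible but not quantified anywhere. Any such bias would run toward no effect, so it would not create a false benefit.

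**Conclusion.** The conflict is real and concerns the primary estimator. The missing-data paragraph promises all pre-dropout data through mixed-effects models, while the aims section names, for the primary and pupil outcomes, a method that in its standard form uses complete participants only.

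The size is uncertain because it depends on two things the documents do not give: how many non-completers leave after at least one session, and how far leaving depends on the withdrawal score. The gain from the mixed model therefore runs from none to about 7 effective participants (23 − 16). The bias range of 0% to about 16% depends on the assumed means, SDs and logistic dropout, and the upper end needs steep dependence. The power comparison also takes SD 20 as the SD of the paired difference.

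The case for changing the text does not depend on the upper end. The mixed model is the method the SAP already endorses, loses nothing in the worst case for it, and removes a choice that could otherwise be made after the data are seen.

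**What to change.** In the SAP's Aims, Outcome Measures, and Hypotheses section, for both the withdrawal score and pupil diameter:

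- Name a linear mixed-effects model with V-MJ dose, naloxone dose and their interaction as fixed effects and participant as a random effect.
- Define the analysis set as every participant with at least one test session.
- State a small-sample degrees-of-freedom method, such as Kenward–Roger.
- Say that the missing-data sensitivity analyses already described apply to this model.
- Report the repeated-measures ANOVA in completers as supportive.

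It would also help to report how many participants leave before session 1 and how many leave after each session, since that determines how much the choice matters.

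The cost is wording: no added participants, sessions or data. The downside is a slightly more complex model that needs the degrees-of-freedom correction at this sample size.

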## **Specific Aims and Hypotheses**

### Specific Aims and Hypotheses

**Primary Aim:** Assess the ability of vaped marijuana to alter the severity of naloxone-precipitated withdrawal. We hypothesize that there will be a dose-dependent effect of vaped marijuana to attenuate the severity of naloxone-precipitated withdrawal.

**Secondary Aim:** Assess the safety of vaped marijuana in combination with naloxone. We hypothesize that vaped marijuana, in combination with naloxone, will produce more AEs than placebo but less than naloxone alone.

**Secondary Aim:** Assess the impact of vaped marijuana on naloxone's effects on pupil diameter (i.e.,  $\mu$ -opioid receptor blockage). We hypothesize that vaped marijuana will not significantly alter naloxone's effects on pupil diameter (in comparison to placebo).

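### The primary ANOVA tests for any difference among the dose conditions, which naloxone alone would almost certainly produce, and no V-MJ comparison is named to decide the primary aim

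*SAP*

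**What the plan says.** The SAP (Aims, Outcome Measures, and Hypotheses, Primary Aim) sets the endpoint: "The primary dependent variable (DV) for this aim will be the total opioid withdrawal score from the testing session". The analysis follows: "Repeated-measures analysis of variance (ANOVA) will be used to assess differences among the various dose conditions". The hypothesis attached to it is directional and about dose: "We hypothesize that there will be a dose-dependent effect of dronabinol to attenuate the severity of naloxone-precipitated withdrawal". The protocol (Specific Aims and Hypotheses) says the same of vaped marijuana, and its Lay Summary adds that "the combined administration (V-MJ + NLX) will produce significantly less withdrawal than NLX alone".

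The conditions are in the protocol's Study Procedures: "The following dose combinations of vaped marijuana (V-MJ) and IN naloxone will be tested in random order". Six follow, formed by crossing naloxone 0 or 4 mg with V-MJ 0, 12.5 or 25 mg. The SAP's Randomization paragraph still describes dronabinol at three levels and naloxone at three other levels, so the two documents do not describe the same set of conditions.

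On multiplicity the SAP's Data Analysis Plan says: "Where needed, False Discovery Rate Analysis will be used to adjust critical p values to control for multiple comparisons". It defines no family of comparisons. The same paragraph states that a comparison in which homogeneity is violated will not be called significant. The Power section is pairwise: a 15-point difference with a mean SD of 20, between any two dose conditions.

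**The concern.** The aim is whether V-MJ reduces withdrawal that naloxone has precipitated. That is a question about V-MJ dose among the sessions with active naloxone. The stated analysis, read literally, asks whether any condition differs from any other. Half of the protocol's conditions contain no naloxone, and participants are selected by a naloxone challenge and tested while stable on morphine. A naloxone effect is therefore expected by design, and the test can reject for that reason alone.

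Two things are at stake. A significant primary analysis could be reported as success although it carries no information about V-MJ. And because no contrast, trend or interaction is designated, the comparison that carries the claim (either V-MJ dose, a trend, a V-MJ main effect or an interaction) could be chosen after the data are seen.

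**Working it through.** **Inputs from the documents.** n = 16 completers, SD 20, a 15-point difference (d = 15/20 = 0.75) and two-sided alpha 0.05 (SAP); six conditions, three without naloxone (protocol, Study Procedures).

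**Assumptions.** The documents do not give the within-person correlation ρ (0.5 used, range 0 to 0.7), the naloxone 4 mg versus 0 mg difference D (5 to 30 points used), or a separate SD for naloxone-active sessions (20 used).

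**1. The SAP's own power figure.** For a paired comparison, the SD of the difference is 20 × √(2(1 − ρ)) = 20 at ρ = 0.5. So dz = 15/20 = 0.75 and the noncentrality is 0.75 × √16 = 3.0 on 15 df. Two-sided power is 80.1%; one-sided it is 88.8%. The SAP states 90%, which two-sided needs ρ of about 0.63. That gap is a separate matter, and the present point does not depend on it.

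**2. The stated test with V-MJ inert.** The condition means are 0, 0, 0, D, D, D. Their squared deviations sum to 6 × (D/2)² = 1.5D². For a one-way repeated-measures ANOVA with 5 and 75 df, λ = n × 1.5D² / (SD² × (1 − ρ)) = 16 × 1.5D² / (400 × 0.5) = 0.12D².

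| D (points) | λ at ρ = 0.5 | P(significant), ρ = 0 | ρ = 0.3 | ρ = 0.5 | ρ = 0.7 |
|---|---|---|---|---|---|
| 5 | 3 | 12% | 16% | 21% | 34% |
| 10 | 12 | 40% | 56% | 73% | 94% |
| 15 | 27 | 79% | 93% | 98.5% | 99.98% |
| 20 | 48 | 97% | 99.7% | 99.99% | >99.99% |

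In simulation at D = 15 and ρ = 0.5, the Greenhouse-Geisser correction gives 97.4%. If the SAP's dose levels were fully crossed into nine conditions, with both active naloxone levels adding 15 points, the figure is 99.5%.

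**3. Does the result distinguish what V-MJ does?** At D = 30 and ρ = 0.5 the test is significant in about 100% of trials whether V-MJ is inert, halves withdrawal at the top dose, abolishes it at both doses, or worsens it. At D = 15 the same four cases give 98.5%, 89%, 84% and 99.98%. Rejection is somewhat less likely when V-MJ works, because attenuation shrinks the spread among the means.

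**4. A comparison that does address the aim.** With V-MJ inert, the simulated paired contrast of V-MJ 25 mg versus 0 mg within naloxone 4 mg rejects in about 5% of trials at every D tried. Its power is:

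- for a true 15 points: noncentrality 3.0, power 80% (66% at ρ = 0.3, 95% at ρ = 0.7);
- for a true 7.5 points, as a linear trend would give at 12.5 mg: dz = 0.375, noncentrality 1.5, power 29%.

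For equally spaced doses 0, 12.5 and 25 the linear contrast has weights −1, 0, 1, so 25 mg versus 0 mg is also the linear dose contrast.

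**The case against.** The best defence is that an investigator would read the ANOVA as a naloxone by V-MJ factorial with follow-up comparisons, that the Lay Summary states the key comparison, and that this is a proof-of-concept study. Part of that stands. The SAP does not use the word omnibus, and a factorial model would supply V-MJ terms. But the SAP specifies no factors and no deciding term. The Lay Summary gives no V-MJ dose, test or multiplicity rule, and the SAP does not carry its comparison over. The SAP's emphasis on effect sizes covers the secondary aims only.

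Four stronger readings are tempting, and the documents do not support them:

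- **That naloxone makes the test significant whatever V-MJ does.** The naloxone effect is an assumption. At 10 points the test rejects in 73% of trials, and at 5 points in 21%. The homogeneity rule could also block significance. If naloxone-free sessions had SD 5 against 20 and the rule meant Mauchly's test (the SAP names none), essentially every simulated trial would violate it.
- **That FDR over all 15 pairs seriously inflates false V-MJ claims.** The SAP does not say that all pairs form the family. Even if they did, the 25 mg versus 0 mg pair within naloxone 4 mg would be falsely rejected in only about 2 to 4% of trials.
- **That a pooled ANOVA error understates the V-MJ standard error.** This needs unequal variances, which the documents do not report, and a six-condition error term for contrasts, which the SAP does not state. The homogeneity rule would also stop many such claims.
- **That the Lay Summary and the Specific Aims conflict.** They do not. Less withdrawal with the combination than with naloxone alone follows from dose-dependent attenuation.

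**Conclusion.** The point holds in this form. The only stated primary analysis is almost certain to be significant from naloxone alone if naloxone raises the score by about 15 points or more. With V-MJ inert, SD 20 and ρ = 0.5 the figure is 98.5% at 15 points, with a range of 79% to 99.98% over correlations 0 to 0.7. A significant result would not show that V-MJ attenuates naloxone-precipitated withdrawal, and nothing in either document names the comparison that would.

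The percentages rest on the assumed naloxone effect, correlation and SD. The absence of a deciding V-MJ comparison rests on the text alone. Because this is the primary analysis, it should be settled before the data are analysed.

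**What to change.** - **Conditions first.** Reconcile the SAP's drug and dose levels with the protocol's list, so that the contrast refers to conditions that are run.
- **Primary comparison.** Pre-specify one V-MJ comparison within the naloxone-active sessions. On the protocol's list, an example is V-MJ 25 mg versus 0 mg within naloxone 4 mg, two-sided 0.05. Test 12.5 mg versus 0 mg, also at 0.05, only if the first is significant. Two multiplicity-adjusted dose comparisons would also be valid; at 0.025 each, power for 15 points falls from 80% to 69%.
- **Model.** Estimate the contrast in the mixed-effects model the SAP already plans for missing data, with contrast-specific (unequal) variance. This uses all available data, where simple paired differences would drop anyone missing one of the two sessions.
- **Other sessions and rules.** Use the naloxone 0 mg sessions for a manipulation check and a secondary estimate of the interaction. Limit FDR to secondary comparisons. State that the homogeneity rule does not block the primary contrast.
- **Power.** Restate it for this contrast with its assumptions: about 80% for 15 points and 29% for 7.5 points, if the SD is 20 in naloxone 4 mg sessions and the correlation is 0.5. The SAP's 20 is a mean SD and is not tied to those sessions. If it were 30 there, dz = 15/30 = 0.5 and power would be about 46%.

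The cost is SAP text plus the reconciliation of conditions; the change itself alters no visit or procedure. The downside is that 12.5 mg can be claimed only after 25 mg succeeds.
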